1.4 Rationale for Current Study

Based on our preclinical findings, we hypothesize that the combination of everolimus and eribulin will have a synergistic effect with a dual inhibition of both AKT and mTOR and will increase clinical activity in patients with metastatic TNBC. Previous studies of each of these drugs in MBC show acceptable toxicity, and we hypothesize that this drug combination could

offer a novel approach to treat patients with metastatic TNBC who are resistant to anthracyclines and taxanes or platinums.

2.0 Specific Objectives

The overall objective of this study is to conduct a phase I/Ib trial of everolimus plus eribulin in metastatic TNBC patients who are resistant to anthracyclines and/or taxanes or platinums. The trial will consist of a Phase I portion and a Phase Ib portion.

2.1 Primary Objective for Phase I Study

The primary objective of the Phase I portion of the study is to determine the safety and tolerability of everolimus and eribulin, and determine the recommended Phase Ib dose (RP2D) of the drug combination in patients with resistant metastatic TNBC.

2.2 Primary Objective for Phase Ib Study

The primary objective of the Phase IB portion of the study is to evaluate the event-free survival (EFS) rate for patients with resistant metastatic TNBC at the RP2D of everolimus and eribulin to determine if the drug combination is worthy of further study.

2.3 Secondary Objectives for Phase Ib Study

The secondary objectives of the Phase Ib portion of the study are to determine response rate, OS, toxicity, and PK for everolimus and eribulin in patients with resistant metastatic TNBC.

A further secondary objective is to collect blood, skin punch biopsies, and tumor biopsies before and after treatment from all patients and perform proteomic analysis to determine the level of inhibition of the PI3K pathway in tumor cells versus non-therapeutic targets.

3.0 Study Endpoints

3.1 Primary Endpoint

The primary endpoints of the study are:

- Phase I: DLT (see **Section 11** for statistical considerations).
- Phase IB: EFS at 4 months (see **Section 11** for statistical considerations).

3.2 Secondary Endpoints

The secondary endpoints are:

- Phase Ib: Response rate, PFS, OS, toxicity profile and PK parameters.

4.0 Study Design

This is a Phase I/Ib trial of everolimus plus eribulin in metastatic TNBC patients who are resistant to anthracyclines and/or taxanes or platinum.

4.1 Phase I Study

The Phase I portion of the trial will use the toxicity equivalence range (TEQR) design. Based on this design, the target equivalence range of dose-limiting toxicities (DLTs) is 0.20-0.35. Toxicity levels of ≥ 0.51 will be considered too toxic, and doses which achieve this level will be stopped. Patients will enter the protocol in cohorts of three. This phase will be considered complete when 12 patients are studied at a single dose level with a toxicity level < 0.51 . The RP2D will be the dose closest to the target of 0.25 below 0.51 based on isotonic regression. Based on these requirements, the TEQR design will use a minimum of 6 patients and a maximum of 24 patients (median of 18) to determine the MTD. (see **Section 11**).

The PMT team for protocol 14036 reviewed the data: dose level 2 was closed after 2 of 3 evaluable participants experienced DLTs an observed rate of 67%; dose level 1, we saw 4 DLTs in 8 evaluable participants giving an observed DLT rate of 50% on this dose. Our equivalence range for DLT rate for this trial is 20-35%, our observed rate of 50% is above 35% so we plan to de-escalate. Two participants experienced grade 4 neutrophil count decrease and 2 experienced mucositis (1 grade 3 DLT, 1 participant received 71% of Everolimus due to grade 2 which is a DLT). Thus, the team decided to amend the protocol to allow for two new dose levels at a lower dose of Eribulin, and start the next cohort of patients at dose level B1.

Dosing Schedule: cycle length is 21 days

Dose level A	Everolimus (oral)	Eribulin (intravenous)
A-1	2.5mg daily (day 1 to 21)	1.4mg/m ² on days 1, 8
A1	5mg daily (day 1 to 21)	1.4mg/m ² on days 1,8
A2	7.5mg daily (day 1 to 21)	1.4mg/m ² on days 1,8
A3	10mg daily (day 1 to 21)	1.4mg/m ² on days 1, 8

Dose level B	Everolimus (oral)	Eribulin (intravenous)
B1	5mg daily (day 1 to 21)	1.1mg/m ² on days 1,8
B-1	2.5mg daily (day 1 to 21)	1.1mg/m ² on days 1,8

4.2 Phase Ib Study

In the Phase Ib portion of the trial, a Simon's Optimal two-stage design will be used to determine if the combination of everolimus and eribulin results in a greater rate of patients who are event-free at 4 months than with eribulin alone. Based on data from the EMBRACE trial, we set the 4-month EFS rate for eribulin at 45%. We want to determine if the drug combination has a 4-month EFS rate of $\geq 70\%$ (25% improvement). Setting both the type I and type II errors to 0.1 after 12 patients (from the MTD at the end of the phase I trial), if ≤ 5 patients are event-free at 4 months, the study will stop for further accrual. If ≥ 6 patients are event-free at 4 months we will enroll 15 more patients for a total of 27 patients at the RP2D. If ≥ 16 patients out of the 27 are

event-free at 4 months we will consider the combination worthy of further study (see **Section 11**).

Patient will be asked to provide a fresh tumor tissue from a newly obtained core or excisional biopsy of a tumor lesion. Newly –obtained is defined as a specimen obtained up to 6 weeks (42 days) prior to initiation of treatment on day 1. Subjects for whom newly-obtained samples cannot be provided (e.g. inaccessible or subject safety concern) may submit an archived specimen only upon agreement from the study PI.

For patients who consented for optional tumor biopsy upon disease progression, a sample of tumor tissue that may be biopsied or resected will also be collected (see **Section 12.2**).

To reduce dose-limiting oral mucositis, a **mandatory dexamethasone mouth wash** (alcohol-free 0.5 mg/5 mL dexamethasone solution) **will be used for primary prophylaxis of oral mucositis (Section 8.1.2)**.

We will assess tumor response using response evaluation criteria in solid tumors (RECIST) Version 1.1 criteria based on radiologic imaging every 2 cycles of treatment (6 weeks).

Toxicity will be evaluated based on the National Cancer Institute Common Terminology Criteria for Adverse Events (NCI CTCAE) v4.0.

Patients enrolled in the expanded cohort at the RP2D will also be asked to undergo serial blood sampling to evaluate the PK of everolimus and eribulin. Although it is unlikely that these two agents will interact negatively, both drugs are substrates for the membrane transporter P-glycoprotein. Therefore, PK studies will be performed in the expanded cohort treated at the RP2D to evaluate the PK of the drug combination (see **Section 12.1**).

For correlative studies, blood will be collected from patients prior to the first dose of everolimus and eribulin, at 4 and 8 hours after the first dose of everolimus and eribulin on day 1, and at two post-dose time points on days 4 and 8 of the first cycle for patients enrolled on the expanded cohort of RP2D and consented for additional research blood collection.

Two sets of optional skin punch biopsies (2 biopsies per set for a total of 4 biopsies) will be performed for patients who consented for skin biopsy for the expanded cohort level.

- First set
 - Biopsy 1 (3mm diameter) will be performed one week prior to any dosing.

- Biopsy 2 (3mm diameter) will be performed on the same site as Biopsy 1 on the day of the first dose of eribulin and everolimus; cycle 1 (prior to any dosing).
- Second set
 - Biopsy 3 (3mm diameter) will be performed on a new site on the day of the first dose of eribulin and everolimus; cycle 1 (prior to any dosing).
 - Biopsy 4 (3mm diameter) will be performed on the same site as Biopsy 3, one week later on the day that the second dose of eribulin is given (prior to dosing).

Patient will be asked to provide a fresh tumor tissue from a newly obtained core or excisional biopsy of a tumor lesion prior to study entry. Newly –obtained is defined as a specimen obtained up to 6 weeks (42 days) prior to initiation of treatment on day 1. Subjects for whom newly-obtained samples cannot be provided (e.g. inaccessible or subject safety concern) may submit an archived specimen only upon agreement from the study PI.

For patients who consented for optional tumor biopsy upon progression, a sample of tumor tissue that may be biopsied or resected and will also be collected (see **Section 12.2**).

Serum, peripheral blood mononuclear cells (PBMC), skin biopsy tissue and tumor tissue will be processed and stored according to established laboratory protocols and stored at -80°C until proteomic analysis. Analysis will be performed by Luminex and mass spectrometry, and western blotting for pAKT (Ser473), and AKT, p4E-BP1 (ser65/Thr70) and 4E-BP1, pS6K1 (Thr389) and S6K1, and pS6 (Ser235/236) and S6 (see **Section 12.2**).

5.0 Patient Eligibility

5.1 Inclusion Criteria

- Patients must have histologically confirmed stage IV TNBC (patients who had metastatic disease within 6 months of lumpectomy or mastectomy for treatment of TNBC may be excused from repeat biopsy).
- Be willing to provide tissue from a newly obtained core or excisional biopsy of a tumor lesion. Newly –obtained is defined as a specimen obtained up to 6 weeks (42 days) prior to initiation of treatment on day 1. Subjects for whom newly-obtained samples cannot be provided (e.g. inaccessible or subject safety concern) may submit an archived specimen only upon agreement from the study PI.
- Patients must have had prior treatment with antracyclines and/or taxanes (resistant) or platinum including adjuvant or neoadjuvant therapy.
 - Both measurable as well as non-measurable disease by RECIST 1.1 will be allowed.
- Patients with chemotherapy for metastatic disease (patients with 0-3 prior lines of chemotherapy for MBC).
- Age ≥ 18 years.
- Life expectancy of ≥ 3 months.

- Performance status: ECOG PS 0-2.
- Adequate bone marrow, liver and renal function as assessed by the following: Hemoglobin $\geq 9.0\text{g/dl}$, absolute neutrophil count (ANC) $\geq 1,500/\text{mm}^3$, Platelet count $\geq 100,000/\text{mm}^3$, Creatinine ≤ 1.5 times the ULN Liver Function Tests: Total bilirubin less \leq to 1 times ULN, ALT and AST \leq to 2.5 times the ULN if no liver metastases. For patients with known liver metastases, AST and ALT must be \leq to 5 times the ULN.
- Women of child-bearing potential must agree to use adequate contraception (hormonal or barrier method of birth control or abstinence) prior to study entry and for up to 8 weeks after ending treatment. Should a woman become pregnant or suspect that she is pregnant while participating on the trial, she should inform her treating physician immediately (see **Section 5.2**).
- Ability to understand and the willingness to sign a written informed consent document.
- Be willing to use dexamethasone mouth wash as directed.

5.2 Exclusion Criteria

- Patients who have had chemotherapy or radiotherapy within 2-weeks prior to entering the study or those who have not recovered from AEs due to agents administered >3 weeks prior to entering the study.
- Patients may not be receiving any other investigational agents.
- Patients with symptomatic brain metastases are excluded from this clinical trial.
- Uncontrolled current illness including, but not limited to, ongoing or active infection ($>\text{Grade 2}$ based on the NCI CTCAE v4.0, symptomatic congestive heart failure, unstable angina pectoris, myocardial infarction within the past 6 months, cardiac ventricular arrhythmias requiring anti-arrhythmic therapy, or psychiatric illness/social situations that would limit compliance with study requirements.
- Pregnant women.
- Prior eribulin use.
- Patients with HIV, chronic hepatitis B, or chronic hepatitis C (known from the existing medical record).
- Concomitant use with strong or moderate CPY3A4/PgP inhibitors and CPY3A4/PgP inducers.
- Women of child-bearing potential (WOCBP), defined as all women physiologically capable of becoming pregnant, must use highly effective methods of contraception during the study and 8 weeks after ending treatment. Highly effective contraception methods include combination of any two of the following:
 - Use of oral, injected or implanted hormonal methods of contraception or;
 - Placement of an intrauterine device (IUD) or intrauterine system (IUS);
 - Barrier methods of contraception: condom or occlusive cap (diaphragm or cervical/vault caps) with spermicidal foam/gel/film/cream/ vaginal suppository;
 - Total abstinence;
 - Male/female sterilization.

Women are considered post-menopausal and not of child-bearing potential if they have had 12 months of natural (spontaneous) amenorrhea with an appropriate clinical profile (e.g. age appropriate, history of vasomotor symptoms) or have had surgical bilateral oophorectomy (with or without hysterectomy) or tubal ligation at least six weeks prior to randomization. In the case of oophorectomy alone, only when the reproductive status of the woman has been confirmed by follow up hormone level assessment is she considered not of child-bearing potential.

- Male patients whose sexual partner(s) are WOCBP who are not willing to use adequate contraception, during the study and for 8 weeks after the end of treatment.
- Noncomplaint with oral medication and/or dexamethasone mouth wash

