Be willing to use dexamethasone mouth wash as directed.

Exclusion Criteria

Patients may not be receiving any other investigational agents; patients received chemotherapy and/radiation therapy within 2 weeks from study entry; patients with symptomatic brain metastases; uncontrolled current illness including, but not limited to, ongoing or active infection (>Grade 2), symptomatic congestive heart failure, unstable angina pectoris, myocardial infarction within the past 6 months, cardiac ventricular arrhythmias requiring anti-arrhythmic therapy, or psychiatric illness/social situations that would limit compliance with study requirements; pregnant women; prior eribulin use; patients with known history of HIV; chronic hepatitis B; or chronic hepatitis C ; Concomitant use with strong or moderate CPY3A4/PgP inhibitors and CPY3A4/PgP inducers is not permitted; patient who is noncompliant with oral medication and mouth wash regimen.

Clinical Observations and Tests to be Performed

Pre-study assessments should be performed within 28 days prior to initiating therapy.

We will assess tumor response using response evaluation criteria in solid tumors (RECIST) Version 1.1 criteria based on radiologic imaging every 2 cycles of treatment (6 weeks).

Toxicity will be evaluated based on the National Cancer Institute Common Terminology Criteria for Adverse Events (NCI CTCAE) v4.0.

Patients enrolled in the expanded phase Ib cohort at the RP2D will also be asked to undergo serial blood sampling to evaluate the PK of everolimus and eribulin. Although it is unlikely that these two agents will interact negatively, both drugs are substrates for the membrane transporter P-glycoprotein. Therefore, PK studies will be performed in the expanded cohort treated at the RP2D to evaluate the PK of the drug combination.

For correlative studies, blood will be collected from patients who consented at the prior time points: prior to the first dose of everolimus and eribulin, at 4 and 8 hours after the first dose of everolimus and eribulin on day 1, and at two post-dose time points on days 4 and 8 of the first cycle for patients enrolled on the expanded cohort of RP2D.

Two sets of optional punch biopsies (two biopsies per set for a total of four biopsies) will be performed on patients who consented as follows:

- First set
 - Biopsy 1 (3mm diameter) will be performed one week prior to any dosing.

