a: Actual body weight will be used for BSA and Eribulin dose calculation. **b:** Pre-study and every two cycles. **c:** Serum pregnancy test (women of childbearing potential). **d:** Albumin, alkaline phosphatase, total bilirubin, bicarbonate, BUN, calcium, chloride, creatinine, glucose, LDH, phosphorus, potassium, magnesium, total protein, SGOT [AST], SGPT [ALT], sodium. **e:** Two sets of punch biopsies (two biopsies per set for a total of four biopsies – Optional for patients who consented at RP2D level) will be performed as follows: First set- Biopsy 1 will be performed one week prior to any dosing (pre-study). Biopsy 2 will be performed on the same site as Biopsy 1 on the day of the first dose of eribulin and everolimus; cycle 1 (prior to any dosing). Second set: Biopsy 3 will be performed on a new site on the day that the second dose of eribulin is given (prior to dosing). **f:** To be performed in a subset of patients enrolled on the Phase Ib portion of the study (see section 12.0). **g:** Staging images (CT scans, bone scan) must be performed within 28 days prior to study entry. **h:** Blood correlative studies will be collected pre-study, before the first dose of everolimus and eribulin, at 4 and 8 hours after the first dose of everolimus and eribulin on day 1, and at two post-dose time points on days 4 and 8 of the first cycle for patients on the expanded cohort of RP2D. **i:** Mandatory tumor biopsy specimen (fresh frozen and/or paraffin-embedded) will be obtained prior to study entry. An optional tumor tissue biopsy will be obtained upon disease progression. **j:** Pre-study assessments should be performed within 28 days prior to initiating therapy, unless otherwise noted. For the on-study treatment, there is a +/- 3 days of window allowed.

Items e, f, h: ONLY for patients enrolled to the expanded cohort, i.e. RP2D.

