8.1.1 Dose Limiting Toxicities

Definition of dose limiting toxicities (DLTs) based on CTCAE 4.0. All toxicities will be attributed to study drug (everolimus) except hematological toxicities. Hematological DLTs will be defined for the combination of eribulin and everolimus. If a hematological DLT occurs, dose reduction or delay will be conducted according to rules defined in 8.1.6 and 8.2.2.

DLT is defined as an AE or abnormal laboratory value as at least possibly related to the study medication and meets any of the criteria per CTCAE 4.0 . The following table is recommended for the most anticipated toxicities.

Decisions to escalate, de-escalate, or expand a dose level will be based on the first course of treatment. To be evaluable for toxicity, a patient must receive at least 1 complete course of treatment (at least 75% of planned dose of both drugs without toxicity) and be followed for at least 21 days (more if there is a dose delay) or have experienced a DLT as defined above. All patients enrolled are to be fully followed for toxicity; any patients who

are not evaluable for toxicity will be replaced. Intra-patient dose escalation is not allowed.

Table 8.1.1a Criteria for defining dose-limiting toxicities.

Toxicity	DLT criteria
Hematology	CTCAE grade ≥ 3 neutropenia lasting more than 7 consecutive days
	CTCAE grade 4 thrombocytopenia
	CTCAE grade 4 neutropenia
	CTCAE Grade 3 neutropenia with fever (temperature $\geq 38.5^{\circ}\text{C}$)
Non-hematology	Any CTCAE grade ≥ 3 AEs with the following exceptions
Exceptions to DLT criteria	Grade 3 alopecia
	Controllable grade 3 nausea and vomiting
	<5 days of CTCAE grade 3 fatigue
	Triglycerides $< 1,500\text{mg/dL}$, which recover within 1 week
	Grade 3 laboratory abnormalities that are correctable to grade 2 or less within 24 hours
	Grade 3 hyperglycemia that is controlled to Grade 2 and under should not be considered DLT. For management of hyperglycemia, please refer to section 8.1.9.
Treatment delays	>2 weeks as a result of unresolved toxicity during the first cycle of therapy (failure of ANC to recover to $\geq 1,000/\mu\text{L}$ or platelets to recover to $\geq 50,000/\mu\text{L}$ within 14 days of the last treatment)
Others	Failure to complete at least 75% of planned dose of either one of the drugs during cycle 1, due to toxicity, will also be considered a DLT.

Follow-up for toxicities.

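### The washout and recovery clauses in Section 5.2 do not meet: treatment given 15 to 21 days before entry falls under neither, so unresolved non-hematological toxicity from it does not exclude a patient and could be counted as a DLT

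*Combined protocol and SAP*

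**What the plan says.** The first exclusion in Section 5.2 joins two time rules. The washout rule excludes "Patients who have had chemotherapy or radiotherapy within 2-weeks prior to entering the study". The recovery rule excludes "those who have not recovered from AEs due to agents administered >3 weeks prior to entering the study". The synopsis exclusion list has only the washout: "patients received chemotherapy and/radiation therapy within 2 weeks from study entry".

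Section 5.1 protects organ function under "Adequate bone marrow, liver and renal function as assessed by the following", followed by limits for hemoglobin, ANC, platelets, creatinine, bilirubin and transaminases. On timing, Section 6.4, footnote j, says: "Pre-study assessments should be performed within 28 days prior to initiating therapy, unless otherwise noted".

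Section 8.1.1 decides what counts as a DLT. It states "All toxicities will be attributed to study drug (everolimus) except hematological toxicities", and it sets the relatedness threshold as "DLT is defined as an AE or abnormal laboratory value as at least possibly related to the study medication". It also counts as a DLT "Failure to complete at least 75% of planned dose of either one of the drugs during cycle 1, due to toxicity". No minimum grade is attached to that last criterion, and nothing is said about toxicity present at baseline.

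**The concern.** The two rules run in opposite directions and leave a week between them. A patient with unresolved mucositis from chemotherapy 16 days ago is eligible, while a patient with the same mucositis from chemotherapy 25 days ago is not. The documents give no reason for admitting the more recently treated patient.

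Two things are at stake. The first is safety: a patient who has not recovered from one regimen can start the combination. The second is the Phase I primary endpoint. DLTs in the first cycle drive every escalation decision, and an event that belongs partly to prior therapy would be read as toxicity of the dose under test. Dose finding is still active, since the next cohort starts at B1.

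**Working it through.** **1. Interval check (Section 5.2).** Count days before entry. Washout excludes days 1 to 14. Recovery excludes day 22 and beyond if the patient has not recovered. Days covered by neither rule: 15, 16, 17, 18, 19, 20 and 21, which is 7 days. The washout names only chemotherapy and radiotherapy, so for other prior agents no recovery rule applies anywhere in the last 21 days.

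**2. Does another criterion close the gap?** The laboratory limits in Section 5.1 address marrow, liver and kidney. They do not screen for mucositis, neuropathy or diarrhea. Section 8.2.1 withholds eribulin on Day 1 for grade 3 or 4 non-hematological toxicity, but only when it is attributed to eribulin, so it does not address prior therapy.

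**3. Route to a DLT (Section 8.1.1).** There are two routes: worsening to grade 3 or more, or receiving less than 75% of either drug because of toxicity. The second has been used at a low grade. Section 11.1.1 records one DLT at dose level 1 in a participant who received 71% of everolimus because of grade 2 mucositis.

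**4. The plan's own decisions, reproduced.** Section 11.1.1 uses cut-offs of 0.20, 0.35 and 0.51.
- Dose level 1: 4/8 = 0.50, above 0.35 and below 0.51, so de-escalate (D), as stated.
- Dose level 2: 2/3 = 0.67, at least 0.51, so closed (DU), as stated.

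**5. Effect of one extra DLT in Table 11.2.**

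| Without | With one more | Change |
|---|---|---|
| 0/3 = 0.00 | 1/3 = 0.33 | E to S |
| 1/3 = 0.33 | 2/3 = 0.67 | S to DU |
| 2/6 = 0.33 | 3/6 = 0.50 | S to D |

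**6. Illustration for a first cohort of 3.** Assume a true DLT rate p = 0.25 (the design target) and let q be the share of the other patients who have a carry-over DLT. The documents give no value for q, so 1%, 5% and 10% are assumptions. The rate as counted is p* = 1 − (1 − p)(1 − q), and the chance of closing the dose is P(2 or more of 3) = 3p*²(1 − p*) + p*³.

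| q | p* | P(2 or more of 3) |
|---|---|---|
| 0 | 0.2500 | 0.141 + 0.016 = 0.156 |
| 0.01 | 0.2575 | 0.148 + 0.017 = 0.165 |
| 0.05 | 0.2875 | 0.177 + 0.024 = 0.200 |
| 0.10 | 0.3250 | 0.214 + 0.034 = 0.248 |

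(Totals are rounded from unrounded terms.)

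**7. Blood counts.** If first dose and entry coincide, a count drawn 22 to 28 days earlier satisfies footnote j and predates chemotherapy given on days 15 to 21. The route is narrow: Section 8.2.1 bars Day 1 eribulin at ANC below 1 × 10⁹/L or platelets below 75 × 10⁹/L. Those holds are looser than the entry limits (1,500 and 100,000/mm³), so they limit the problem without removing it.

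**The case against.** The strongest reply is that the gap is real on paper but hardly matters for the DLT count.

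- **Attribution is not automatic.** A DLT must be at least possibly related to study medication. Section 10.3 defines an AE as a new event or a change in an existing condition, so an unchanged baseline toxicity is arguably not an AE. Section 10.8 asks for timing, underlying disease and other treatment to be weighed. The sentence assigning toxicity to everolimus can be read as dividing events between the two study drugs. This stands, and it is why the point is put as something that could happen. It does not settle the matter, because low-grade toxicity that worsens or interrupts dosing is a change, and possible relatedness is a low bar.
- **Few patients can contribute.** A patient must have been last treated in a 7-day window, be unrecovered, and then meet a DLT criterion. For q to reach 5%, one third of patients would have to fall in the window and 15% of those carry over a DLT (1/3 × 0.15 = 0.05). This stands; the 1% row may be nearer the truth, but the documents cannot say.
- **Severe residual toxicity might be caught** by the exclusion for uncontrolled current illness. That is discretionary and does not address milder toxicity.

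Two stronger readings are tempting and are not supported. A reader might infer that the DLTs at dose level 1 (two mucositis, two grade 4 neutropenia) were carry-over. Nothing links them to prior therapy, and the protocol describes both as known drug effects: oral ulceration or mucositis in 44% to 70% on everolimus, usually within a month (Section 8.1.2), and grade 4 neutropenia in 24.1% on eribulin (Section 1.2.1). Removing one would give 3/8 = 0.375, still D; two would have to go to reach 2/8 = 0.25 and S.

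A reader might also infer from Table 11.2 that a step from 4/12 to 5/12 (S to D) changes the dose assigned. Under Section 11.1.1 the phase ends at 12 participants on one level with a rate below 0.51. Both 4/12 = 0.33 and 5/12 = 0.42 meet that, so accrual ends either way and the RP2D goes to isotonic regression.

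**Conclusion.** The wording gap is certain: 7 days before entry fall under neither rule, and no other criterion closes it for non-hematological toxicity. That such toxicity could be counted as a DLT follows from Section 8.1.1 as written. How often it would be is unknown.

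The size is therefore conditional. One misattributed event is enough to change the decision at 0/3, 1/3 or 2/6. At an assumed true rate of 25%, the chance of closing a dose on its first cohort rises by about 0.01 at q = 1%, 0.04 at 5% and 0.09 at 10%. No sample size, type I error or power figure in the plan changes. The documents do not support saying that the dose level 1 result or the decision to de-escalate was distorted. The change is worth making because it is cheap and bears on both safety and the Phase I endpoint.

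**What to change.** Reconcile the washout and recovery clauses in Section 5.2, and the matching line of the synopsis, so that no prior treatment date falls between them. Which interval applies is a clinical choice for the sponsor; the statistical requirement is only that the clauses meet and that the two places agree.

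As a minor addition, clarify in Section 6.4, footnote j, that the laboratory values used for eligibility should postdate the last prior anticancer treatment. The Day 1 ANC and platelet hold in Section 8.2.1 already limits the hematological route, so this matters less.

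The cost is a phrase in each place and an edit to the eligibility checklist. The downside is that a few patients may start up to about a week later or repeat a blood draw.
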